7.1.6 Interactive text messaging

At the end of every 30 days of the study, participants will be asked to evaluate the usability of the text messages in past previous month using Likert scale rating. The response will determine the type of messages the participant will receive subsequent month.

7.2 Training of research assistants and piloting

Training of research assistants and enumerators will take 3 days. On day 1, the research assistants will be introduced to the research methods in a step-by-step approach as shown below. This phase of training will be conducted either online or face-to-face to allow for flexibility during the COVID crisis.

Step 1. Informed consent procedure, research ethics and regulatory requirements and documentation.

Step 2. Participant recruitment and retention strategies

Step 3. Review of the data collection tools, including the socio-demographic and health history questionnaire, food frequency questionnaire and the self-perceived food literacy questionnaire. This step is meant to give the research assistants and enumerators a broad understanding of the expected each tool. All questions in the three tools shall be read and discussed to provide an opportunity for clarification on possible responses.

Step 4. Video illustrations of study-related anthropometric assessments: height, weight, waist and hip circumferences and body composition.

On day 2, the research assistants will be provided with hands-on training on procedures that shall be applied in this study. This phase shall apply didactic approach, face-face demonstrations, and role plays. The trainers

will use actual data collection tools, PowerPoint slides and videos during these structured sessions. The following steps shall be followed in this phase of training:

Steps 1: Role playing of the interviewer-administered data collection tools.

Step 2: Demonstration and breakout sessions for role playing of anthropometric assessments.

On day 3, the socio-demographic and health history questionnaire and the self-perceived food literacy scale will be piloted in hospitals that will not be included in the study. The pilot will include a sample size of 6 respondents, representing 10% of the of the sample projected for the trial, as suggested by Connelly *et al.*, (110)

7.3 Management of data quality during fieldwork

To ensure accurate and reliable data collection, the following measures shall be applied:

- i. Timely provision of data collection tools and equipment to the enumerators and research assistant
- ii. Early logistical arrangements, coordinated by the PI and Co-PI in collaboration with the hospital in-charges
- iii. Coordinating with hospital in-charges regarding arrival and data collection points of enumerators
- iv. Identifying sampled respondents, coordinated by the hospital in-charges
- v. Preparation for collection, with brief overview of steps by the Co-PI and research assistant.

Additionally, data quality during field work shall be ensured by the following activities planned by the Principal Investigator (PI) MM, in collaboration with the Co-Principal Investigators (CO-PIs):

- i. Prepare, conduct, and administer the research budget, and trainings in compliance with applicable laws, regulations and institutional policy governing the conduct of the study.
- ii. Ensure that procedures in the study are consistent with sound research design and do not unnecessarily expose participants to risk or harm.
- iii. Define and communicate roles and responsibilities for each research team member.
- iv. Regularly meet with the CO-PIs and research team to keep them informed of the status of project activities.
- v. Ensure the integrity and safeguarding of research data records and scientific data.
- vi. Ensure the completion, accuracy and timeliness of research data and reports.

JKUAT shall provide permission to conduct the study and provide overall supervision of the study through the Project Lead (FK) Legume Centre of Excellence for Food and Nutrition Security (LCEFONS).

KU Leuven shall provide supervision and administration of the study's research budget, and trainings in compliance with applicable laws, regulations and institutional policy governing the conduct of the study of the study through the Co-PIs (CM and RV).

7.4 Ethical issues

This study will be conducted in respect to the principles contained in the Declaration of Helsinki (111). A written informed consent will be obtained from all participants prior to their enrolment into the study (Appendix 1). The informed consent will allow the participant enough time to decide whether to be in the research study and to make that decision without any pressure from the researchers. Participants will also have the right to refuse to be in the study at all, and to stop participating at any time after study begins.

Study personnel shall ensure strategies to protect privacy interests relating to contact with potential participants, and access to private information at all times during the study. All study personnel shall sign and adhere to the Data Confidentiality Agreement for Study Staff (Appendix 6).

To ensure confidentiality, that an information disclosed by the participants shall not be divulged to others without permission in ways that are inconsistent with the understanding of the informed consent form. During consenting, subjects shall be informed of the precautions that will be taken to protect the confidentiality of the data and be informed of the parties who will or may have access.

The community engagement strategy shall ensure that the study will be conducted in a way that is respectful to individuals and communities to maximize social value. Additionally, internationally recognized standards of good practice with responsiveness to the local context (112) shall be adhered to.

The data from the study will be stored in a secure server where only authorized individuals will have access to the data. The parties will retain the data for 10 years after study completion, according to the General Data Protection Regulation (GDPR) (113). However, neither party will destroy information without first informing the other parties. In case of future testing, permission to conduct further studies shall be sort from the participants.

This study will seek the following approvals, permissions, and registration:

- Letter of support from Jomo Kenyatta University of Agriculture and Technology;
- Ethical approval from the African Medical Research Foundation-Ethics & Scientific Review Committee (AMREF-ESRC);
- Research permit from the National Council for Science Technology and Innovation (NACOSTI);
- Registration of clinical studies with human subjects that assess biomedical and/or health outcomes at clinicaltrials.gov (114).
- Study permit for permission to conduct the study through the Department of Health in Nakuru County.

8 Data Processing and Analysis

8.1 Data coding, entry, and editing; transcription of qualitative data generated

The data will be collected by use of electronic forms. Data shall be collected and stored in a secure cloud server, hosted at the Jomo Kenyatta University of Agriculture and Technology (JKUAT).

8.2 Plan for analysis of quantitative data

Quantitative data will be analyzed by the intention to treat principle (115). Various patient characteristics and primary outcome measures, including anthropometric and biochemical measurements (HbA1c, FBG, lipid profiles) at baseline will be summarized using descriptive statistics. The descriptive statistics will include means and standard deviations for continuous variables and proportions for categorical variables.

HbA1c levels will be compared at 3-months between the two arms using an ANCOVA which will control for baseline HbA1c levels. The intervention and the control groups will be followed-up for six months. One-way and interactive text messaging data will be analyzed descriptively.

A subgroup analyses per hospital and participant socio-demographics including age, sex, education, and income levels will be conducted. All statistical analyses will be performed using R version 4.0.3 (116).

9 Plan for communicating findings of the study

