6.3 Sample size

Hypothesis testing was not the objective of this study. However, for an effect size of 0.60, at a power of 0.80 and at an alpha level of 0.05, a sample size of 25 in each group has been used to results in a 1% reduction of HbA1c levels at post-test compared with pre-test (100). We therefore determined a sample size of 60 a-priori (n=30 intervention, n=30 control arm) to assess feasibility of text messaging in optimizing glycemic control. It is anticipated that this proof-of-concept study will obtain parameters that will be used in determining a robust power calculation for a fully powered efficacy trial, as it has been applied elsewhere in Bucci *et al.* (101).

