6.4 Sampling design

Nakuru county has 18 level 4 hospital(102). Purposive sampling will be used to select two hospitals, one in a rural setting, and another in an urban setting. Multistage random sampling with then be applied to randomly assign 15 participants in either the intervention or control arms using simple random sampling in each of the selected hospitals.

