6.6 Randomization

We will apply simple random sampling through a computer-generated list of random numbers. The hospital diabetes registers from the two selected hospitals will be used to select patients on regular diabetes care from the hospital patient records. The patients will then be assigned numbers and randomly selected.

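### The primary ANCOVA leaves out hospital, although patients are assigned to arms within two deliberately different hospitals (minor loss of precision)

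*Protocol*

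**What the plan says.** Section 8.2 fixes the primary comparison: "HbA1c levels will be compared at 3-months between the two arms using an ANCOVA which will control for baseline HbA1c levels". The abstract also names analysis of covariance without a hospital term. Hospital appears in section 8.2 only as a subgroup factor: "A subgroup analyses per hospital and participant socio-demographics including age, sex, education, and income levels will be conducted".

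The design in section 6.4 is built on hospital. It will "select two hospitals, one in a rural setting, and another in an urban setting", and then "randomly assign 15 participants in either the intervention or control arms using simple random sampling in each of the selected hospitals". Section 6.3 plans 60 patients, 30 per arm. Fifteen per arm per hospital is the only reading that gives this total: 15 × 2 arms × 2 hospitals = 60. Section 6.6 says only "We will apply simple random sampling through a computer-generated list of random numbers" and does not confirm that balance, so both possibilities are examined below.

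**The concern.** When patients are assigned within hospitals, the usual analysis compares the arms within hospitals too. The stated model does not. The two hospitals were chosen to contrast, and under section 7.1.5 each has its own phlebotomist and centrifuge, so a difference in 3-month HbA1c is possible.

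With allocation balanced inside each hospital, the hospital difference cancels out of the estimated treatment effect. The model without hospital still counts that difference as noise, so its standard error is too wide and its test conservative. With allocation not balanced within hospital, the standard error is valid but precision is still lost.

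Two things are at stake: the width of the interval in a 60-patient trial, and the residual SD. Section 6.3 says the trial is meant to supply parameters for a later power calculation, and the residual SD is one of them.

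**Working it through.** **The plan's own figure.** Section 6.3 cites this calculation, per group: "for an effect size of 0.60, at a power of 0.80 and at an alpha level of 0.05, a sample size of 25 in each". For a pre-post (paired) comparison, the normal approximation gives n = ((1.960 + 0.842)/0.60)² = 21.8, and the paired t-test gives 23.8, so 24. That is within one of the stated 25 and fits the section's reference to post-test against pre-test. A comparison of two arms would need 44 to 45 per group (two-sided). That mismatch is a separate matter. It is relevant here only because the SD below comes from the same sentence.

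**Inputs.**
- 60 patients, 30 per arm (6.3), and 30 per hospital (from 6.4).
- SD of HbA1c: 1/0.60 = 1.67, from the 1% change and effect size 0.60 in 6.3. This is an inference.
- Baseline to 3-month correlation: 0.6 assumed, with 0.4 to 0.8 as the range. The protocol gives none.
- d, the hospital difference in 3-month HbA1c left after baseline adjustment: not given, so taken as 0 to 1.5 points.

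**Formula, balanced allocation.** The residual SD is 1.67 × √(1 − 0.6²) = 1.336. Leaving hospital out adds 60 × d²/4 to the residual sum of squares, spread over 57 degrees of freedom. Hence

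SE ratio = √[1 + (d²/4)/1.336² × 60/57].

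- d = 0.5: √(1 + 0.0350 × 1.053) = 1.018
- d = 1.0: √(1 + 0.1401 × 1.053) = 1.071
- d = 1.5: √(1 + 0.3151 × 1.053) = 1.154

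**Simulation** (20,000 trials per scenario, ANCOVA without → with hospital, true effect 1% for power):

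| d | SE too wide by (15:15 per hospital) | Type I error (15:15) | Power (15:15) | Power (30:30 overall only) |
|---|---|---|---|---|
| 0 | 0 | – | 80.3% → 80.3% | 80.0% → 79.3% |
| 0.25 | 0.4% | – | 80.3% → 80.7% | – |
| 0.5 | 1.8% (0.353 vs 0.347) | 4.8% → 5.2% | 79.5% → 80.5% | 79.5% → 79.7% |
| 1.0 | 7.0% | 3.6% → 4.9% | 76.5% → 80.7% | 75.1% → 80.0% |
| 1.5 | 15% | 2.4% → 4.8% | 71.4% → 80.5% | 69.1% → 79.7% |

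A dash means the figure is not reported here. Simulation error on a power near 80% is about √(0.8 × 0.2/20,000) = 0.3 points. Without balance inside hospitals, type I error is about 5% with or without the term.

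**Sensitivity.** Across correlations 0.4 to 0.8 (balanced), the SE is 1.4 to 3.2% too wide and 0.5 to 1.1 points of power are lost at d = 0.5. At d = 1.0 the figures are 5.3 to 12.2% and 2.4 to 4.1 points.

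**Independent check in residual-SD units.** With a hospital difference of 0.5 residual SD, the variance rises by (0.25/4) × 60/57 = 6.6% and the SE by 3.2%, as if 60/1.066 = 56 patients had been analysed. At 1.0 residual SD, the variance rises by 26% and the SE by 12.4%, equivalent to 47.5 patients. For an arm effect of 0.6 residual SD, simulated power is then 0.53 without hospital and 0.62 with it. These powers are lower than in the table because the assumed effect is smaller (0.6 against 1/1.336 = 0.75 residual SD).

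**Planning a later trial.** Sample size scales with variance. Taking the residual variance directly from the stated model would raise a later trial's size by 0.0350 × 1.053 = 3.7% at d = 0.5 and by 0.1401 × 1.053 = 15% at d = 1.0.

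**The case against.** The strongest case against is that this is a refinement and not an error. A baseline-adjusted comparison is valid in a two-hospital trial, and a short protocol sentence need not list every covariate, since a statistical analysis plan could add hospital. That plan is not at hand. But the protocol does state its primary model and covariate and gives hospital a subgroup role only, so the text as written is open to comment.

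The size depends wholly on d, and a rural–urban contrast does not establish one. This stands. Baseline HbA1c also absorbs part of any constant difference D between the hospitals: at a slope of 0.6, at most about 0.4 × D remains. A d of 0.5 would then need D of about 0.5/0.4 = 1.25 points, and a d of 1.0 about 2.5 points, unless the hospitals diverge during follow-up. The larger rows of the table are therefore illustrative.

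The SD is also open to doubt. If 1.67 is the SD of change, as the paired reading of section 6.3 suggests, the cross-sectional SD is 1.67/√(2 × 0.4) = 1.87 and the residual SD 0.8 × 1.87 = 1.49. SE inflation then falls to about 1.5%, 6% and 12.5% at d = 0.5, 1.0 and 1.5, and power for a 1% effect is about 72%. The loss is somewhat smaller but does not disappear.

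Finally, section 6.3 says hypothesis testing is not the objective, which makes power a weak yardstick. Interval width and the residual SD still matter for the stated aim of planning a larger trial. The hospital subgroup analysis would show a difference but would not correct the primary standard error or residual SD.

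**Conclusion.** The point holds and is minor. The stated primary model does not follow the groups within which patients are assigned, and precision is lost if the hospitals differ after baseline adjustment. The loss is nil at d = 0, about 2% in SE and one point of power at d = 0.5, and about 7% and four points at d = 1.0. These figures assume an SD of 1.67, a correlation of 0.6 and balanced allocation within hospital. Validity is not threatened: there is no bias, and the test is at worst conservative. For the protocol's 0.3% target, power is about 8 to 14% across the scenarios with or without the term, so adding hospital does not change what the trial can show there.

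**What to change.** In section 8.2, state that 3-month HbA1c will be compared between arms by ANCOVA with arm, baseline HbA1c and hospital as fixed effects. Fixing this before data are seen also avoids a later choice of covariates. The recommendation is the same whether or not allocation is held to 15 per arm in each hospital.

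The cost is one phrase and one residual degree of freedom (57 to 56), which widens the interval by about 0.04% if the hospitals do not differ and allocation is balanced. In that case there is no power cost. If allocation is not balanced within hospital and the hospitals do not differ, the cost is about 0.7 points of power (80.0% to 79.3%).

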9.1 Dissemination strategy

Findings from the study shall be disseminated through print and electronic media to relevant stakeholders. Foreseen stakeholders include the Kenyan Ministry of Health, the county governments, NACOSTI and AMREF Ethics & Scientific Review Committee (ESRC) and the Jomo Kenyatta University of Agriculture and Technology website. The research findings will also be disseminated through a peer reviewed research publication.

9.2 Outline for research report

The research report that shall be disseminated to various stakeholders will be composed of five sections: introduction, key findings, conclusion, and recommendations for future actions. The findings from this study shall also be published in peer reviewed scientific paper, and shall follow the CONSORT guidelines(117).

9.3 Involvement of stakeholders in the study

The county government has been made aware of the study in earlier contacts and correspondences in our earlier study (AMREF-ESRC P752/2020). Further, findings from this study will be provided to participants through online and physical meetings where applicable. The Ministry of Health national technical working group on nutrition and the County Government of Nakuru will be provided with a research report. A

dissemination meeting shall be held in collaboration with the county government and other relevant stakeholders such as community leaders, hospital staff and other organizations supporting diabetes care.

9.4 Likely policy implications that might arise from the study

This being a pilot, the study seeks to generate information on the feasibility of using mHealth to optimize glycemic control and dietary behavior. The findings of the study may also be used by researchers to design larger studies on mHealth in LMICs. The findings may be of value to the county governments and the Kenyan Ministry of Health in development of policies and guidelines on type 2 diabetes and the patient organizations, including the Kenya Defeat Diabetes Association. Study Limitations and Risks

9.5 Limitations of the study design and methods of data analysis

This is a proof-of-concept study, which is therefore limited by the sample size and restricted generalizability.

9.6 Major assumptions in the study

The main assumption in this study is that participants will be willing to take actions aimed at improving their glycemic control. Secondly, it is assumed that the participants will be willing to receive, read and apply the messages disseminated through their mobile phones.

10 Management and Organization of the Study

The management and organization of this study is a collaborative organization between JKUAT and KU Leuven.

10.2 Other resources and facilities that will be availed for the study

The resources that will be availed for the study have been listed in the budget in Table 3. below.

Additionally, a vehicle will be availed during the study for transportation of study personnel and samples.

10.3 Schedule of activities

The study timelines are listed in Table 3 below

It is planned that the study will begin on 15 July 2021 to

Table 4. Schedule of Activities

	Wk 0	Wk 1	Wk 2	Wk 3	Wk 4	Wk 5	Wk 6	Wk 7	Wk 8	Wk 9	Wk 10	Wk 11	Wk 12	Wk 25
Planned Activity	23-Aug	30-Aug	06-Sep	13-Sep	20-Sep	27-Sep	04-Oct	11-Oct	18-Oct	25-Oct	01-Nov	08-Nov	15-Nov	14-Feb
Recruitment and allocation														
Baseline data collection														
Introduction call and text messages														
Intervention month 1														
Intervention month 2														
Intervention month 3														
Post-Intervention follow-up														

10.4 Budget

The total budget for the entire study is estimated to cost Kes 2,550,320 as tabulated below

Table 5. Budget

Ethics Review Fees and Research Permit				
Item	Units	Unit Cost	Frequency	Total Cost (Ksh)
AMREF Ethics review	1	5000	1	5,000
NACOSTI Research Permit	1	2000	1	2,000
Sub total				7,000
Mobilization and planning				
Item	Units	Unit Cost	Days	Total Cost
Community Mobilizer	6	2,540	1	15,240
Airtime for mobilization	6	500	4	12,000
Sub total				27,240
Lab test Equipment				
Item	Units	Unit Cost	Frequency	Total Cost
Plain Tubes for Serum Zinc Collection	2	1,200	1	2,400
Vacutainer needles (100pcs) Gauge 21	2	1,400	2	5,600
Alcohol swabs (100pcs)	1	420	2	800
Micro pore Tape	1	400	1	400
Disposable Rubber Gloves (Dust free 100pcs)	1	1,000	2	2,000
Test Strips for Cholesterol Metre (25pcs)	5	2,500	2	25,000
Test Strips for Glucometer (50pcs)	3	1,600	2	9,600
Biohazard Safety Box	1	300	1	300
Red Disposable bags (Big)	5	50	1	250
Red Disposable bags (small))	10	30	1	300
Hand Sanitizers (500ml)	5	500	1	2,500
Mask (50pcs)	5	800	1	4,000
Cryol Vial (100pcs)	3	1,000	1	3,000
Sub total				56,150
Equipment for Handling, Transfer and Storage of Blood Samples				
Item	Units	Unit Cost	Frequency	Cost
Refill of Nitrogen Tank with liquid nitrogen 47lit	47	480	1	22,560
Sub total				22,560
Stationery Costs				
Item	Units	Unit Cost	Frequency	Cost
Printing paper	5	500	2	5,000
Pens	15	15	2	450
Sub total				5,450
Lab test costs				
Item	Pts	Unit Cost	Frequency	Cost
HbA1C	60	2949	3	530,820
Lipid Profile	60	2949	3	530,820
Total Cholesterol, Serum	60	949	3	170,820
Sub total				1,232,460
mHealth Costs				

Item	Pts	Unit Cost	Frequency	Cost
Setting up Charges	-	20,000	1	20,000
Maintenance Costs	-	20,000	1	20,000
Bulk SMS Services: Intervention Arm	30	5	48	7,200
Bulk SMS Services: Control Arm	30	5	4	600
Audio Calls: Intervention	30	5	12	18,000
Sub total				65,800
Study monitoring				
Item	Pax	Unit Cost	Frequency	Cost
Per Diem (Principal Investigator)	1	7,640	20	152,800
Per Diem (PhD researcher)	1	7,640	30	229,200
Per Diem (Driver)	1	5,135	30	154,050
Sub total				536,050
Personnel				
Item	Pax	Stipend	Days	Cost
Phlebotomist	2	7,640	14	213,920
Enumerators	4	2,540	14	142,240
Enumerator's transport	6	1,000	2	12,000
Research Assistant	1	795	90	71,550
Community Mobilization	2	2,540	14	71,120
Sub total				510,830
Transport				
Item	Cars	Unit Cost	Frequency	Cost
Fuel Costs	1	10,000	2	20,000
Sub total				20,000
Grand Total				2,483,540

11 References

